### **7.3.4 *Prior Therapy Agents***

Prior systemic cancer therapy (regimen setting, number of regimen, line of therapy, best response to latest regimen etc.) will be summarized and listed by subject.

Prior radiotherapy (Yes/No) and prior surgery (Yes/No) will be summarized and listed by subject.

### **7.3.5 *Physical Examinations***

Subjects with abnormal baseline physical examination will be listed by subject.

### **7.3.6 *Baseline Physical Measurements***

Baseline physical measurements will be listed by subject.

## **7.4 *Extent of Exposure***

Listings will include all available exposure data. Analyses will be performed on all treated subjects, unless otherwise specified.

The treatment period consists of two phases:

- 2 weeks of monotherapy lead-in (Cycle 0) during which single oral daily dose of BMS-986205 monotherapy is administered daily, and
- 48 weeks of combination therapy whereby each treatment cycle is 4 weeks and is comprised of daily doses of BMS-986205 and 1 dose of nivolumab administered every 4 weeks on Day 1 of the treatment cycle up to 12 cycles.

All participants completing approximately 48 weeks of combination study therapy with ongoing disease control (CR, PR, or SD) may be eligible for an additional 48 weeks of study therapy at the originally assigned dose regimen beyond the initial 48 weeks.

The cycle start date will correspond to the dosing date. Extent of Exposure will be assessed separately for the 2-week lead in period for mono BMS-986205 and the drugs in combination.

### 7.4.1 Administration of Study Therapy

The following parameters will be summarized (descriptive statistics) by phase and study therapy:

- Number of doses received
- Cumulative dose (mg) = the sum of all actual doses that a subject received
- Duration of study therapy (weeks)
- Dose intensity (mg/weeks) = cumulative dose (mg) / duration of therapy (weeks)
- Relative dose intensity (%)
- Relative dose intensity (%) using the following categories: < 50%; 50 - < 70%; 70 - < 90%; 90 - < 110%; ≥ 110%

Exposure parameter derivation for each treatment are shown in Table 7.4.1-1.

**Table 7.4.1-1: Administration of study therapy: definition of parameters**

| Parameter                        | BMS-986205  | Nivolumab                                   |
|----------------------------------|---|---|
| Dosing schedule per protocol     | 100 mg QD   | 480 mg Q4W                                  |
| Cumulative Dose (mg)             | Cum dose (mg) is sum of the doses (mg) administered to a subject during the treatment period. |   |
| Duration of study therapy (week) | (Last dose date - Start dose date + 1) / 7  | (Last dose date - Start dose date + 28) / 7 |
| Dose intensity (mg/week)         | Cum dose (mg) / Duration of Therapy (week)  |   |
| Relative dose intensity (%)      | [Dose Intensity / (100 × 7)] × 100  | [Dose Intensity / (480 / 4)] × 100          |

A by-subject listing of dosing of study medications (record of study medication, infusion details, and dose changes) and a by-subject listing of exposure parameters (number of doses, duration of therapy, cumulative dose, dose intensity, and relative dose intensity) will be also provided.

### 7.4.2 Modifications of Study Therapy

#### 7.4.2.1 Dose Delays

Each BMS-986205 and nivolumab may be delayed.

A dose of nivolumab will be considered as actually delayed if the delay is exceeding 3 days (i.e. greater than or equal to 4 days from scheduled dosing date) for nivolumab/IDO1 inhibitor.

BMS-986205 is administered as a tablet daily. A dose of BMS-986205 will be considered as actually delayed (interrupted) if BMS-986205 was not administrated for at least 1 day. Interruption means the continuous oral dosing was stopped or held for a period of time prior to resuming.

All study drugs must be delayed until treatment can resume. Reason for dose delay will be retrieved from CRF dosing pages.

The following parameters will be summarized by study drug:

- Number of subjects with at least one dose delayed, the number of dose delays per subject, the reason for dose delay and the length of dose delay.

#### **7.4.2.2 *Infusion Interruptions and Rate Changes***

Each nivolumab infusion can be interrupted and/or the IV infusion rate can be reduced. This information will be retrieved from CRF dosing pages.

The following parameters will be summarized:

- Number of subjects with at least one dose infusion interruption, the reason for interruption, and the number of infusion interruptions per subject.
- Number of subjects with at least one IV infusion rate reduction, the reason for reduction and the number of infusion with IV rate reduction per subject.

#### **7.4.2.3 *Dose Escalations***

Dose escalations (within subject) are not permitted for nivolumab.

#### **7.4.2.4 *Dose Reductions***

Dose reductions (within subject) are not permitted for nivolumab/IDO1 inhibitor.

Number of subjects with at least one dose reduction, the reason for dose reduction, and the number of dose reductions per subject will be summarized for BMS-986205 only.

#### **7.4.2.5 *Dose Discontinued***

Number of subjects with dose discontinued along with the reason will be summarized by study drug.

#### **7.4.3 *Concomitant Medications***

Concomitant medications, defined as medications other than study medications which are taken at any time on-treatment (i.e. on or after the first day of study therapy and within 100 days following the last dose of study therapy), will be coded using the UMC WHO Drug Global Dictionary.

A by-subject listing of concomitant medications will be provided..

Prior medications, defined as non-study medications with a start date before consent date, and current medications, defined as non-study medications with a start date before the first date of study medication and stop date after consent date, will be coded using the UMC WHO Drug Global Dictionary.

A by-subject listing of prior/current medications will be provided..

#### **7.4.3.1 *Immune modulating medication***

Immune modulating concomitant medications are medications entered on an immune modulating medication form or available from the most current pre-defined list of immune modulating medications. The list of anatomic class, therapeutic class and generic name used for the selection at the time of the database lock will be provided.

A by-subject listing of concomitant immune modulating medications will be provided.

#### **7.4.3.2 *Subsequent Cancer Therapy***

A by-subject listing of subsequent cancer therapy (systemic anti-cancer therapy, radiotherapy and surgery) will be produced for all treated subjects.

### **7.5 *Efficacy***

Analyses in this section will be tabulated for all treated subjects, unless otherwise specified.

#### **7.5.1 *Analysis of Objective Response Rate***

One of the objectives of the study is to estimate the ORR per investigator among all treated subjects. ORR with corresponding 2-sided 95% CI based on the Clopper and Pearson method will be presented.

The number and percentage of subjects in each category of BOR per investigator (complete response [CR], partial response [PR], stable disease [SD], progressive disease [PD], or unable to determine [UTD]) will be presented. Estimates of response rate, along with its exact two-sided 95% CI by Clopper and Pearson will be presented.

A by-subject listing of best overall response will be presented including best overall response per investigator and dates of CR/PR/progression.

A by-subject listing of lesion evaluations per investigator will be presented.

A by-subject listing of per time point tumor response per investigator will be also presented.

#### **7.5.2 *Duration of Response***

Duration of response (DOR) will also be evaluated for subjects who achieved confirmed PR or CR. The DOR will be estimated using the Kaplan-Meier (KM) product limit method and will be displayed graphically. A table will be produced presenting number of events, number of subjects involved, medians, and 95% CIs for the medians. Median values of DOR, along with two-sided 95% CI will be computed based on a log-log transformation method.

A by-subject listing will be presented including best response, duration of response, whether the subject was censored for duration of response, and, if so, the reason.

### **7.6 *Safety***

Analyses in this section will be tabulated for all treated subjects by phase (monotherapy lead-in, combination) and overall, unless otherwise specified.

### **7.6.1      Deaths**

Deaths will be summarized:

- All deaths, reasons for death.
- Deaths within 100 days of last dose received, reasons for death.

A by-subject listing of deaths will be provided for the all enrolled subjects population.

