Adverse Event Reporting and Concomitant Medication Assessments				
Monitor for Nonserious Adverse Events	X	X	X	Nonserious AEs will be collected starting with the first dose of study drug and through 100 days post last dose of study drugs (or 30 days if participant only received BMS-986205).
Monitor for Serious Adverse Events	X	X	X	All SAEs must be collected from the date of participant's written consent until 100 post last dose of study drugs (or 30 days if participant only received BMS-986205) or participant's participation in the study if the last scheduled visit occurs at a later time. SAEs reported in the BMS EDC should be approved within 5 business days of entry.
Concomitant Medication Assessments	X	X	X	
Sample Collection				
PK/ADA Assessments	X	X		See Section 9.5.2 .
Efficacy Assessments				

[figure not shown]
Table 2-4: Follow-Up Procedure Outline (CA017076)

[figure not shown]
Procedure	Clinical Safety Follow-Up ^a			Notes
	FU 1 30 days (\pm 10 days)	FU 2 60 days (\pm 10 days)	FU 3 100 days (\pm 10 days)	
Tumor/Response Assessments			X ^b	Diagnostic imaging by method used at baseline, an unconfirmed PR or CR must be confirmed at least 4 weeks after initial assessments.
New Subsequent Anti-Cancer Therapies	X	X	X	Any new anti-cancer therapies (including surgery and radiotherapy) will be recorded.

[figure not shown]
^a Follow-up visits at Days 30, 60, and 100 (\pm 10 days) should occur after the last dose of study drugs (or at Day 30 if participant only received BMS-986205) or should coincide with the date of discontinuation \pm 10 days if date of discontinuation is greater than 30 days after the last dose to monitor for adverse events.

[figure not shown]
^b Only participants who have not discontinued study treatment for progressive disease.

[figure not shown]

[figure not shown]

[figure not shown]

[figure not shown]
Revised Protocol No.: 01

[figure not shown]
Date: 10-Oct-2018

[figure not shown]
39

[figure not shown]

[figure not shown]

[figure not shown]

[figure not shown]

[figure not shown]

[figure not shown]

[figure not shown]

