Participants who discontinue the treatment phase will enter the Clinical/Safety Follow-Up period. Participants must be followed for at least 100 days after the last dose of study therapy or 30 days if participant only received BMS-986205. Follow-up visits should occur at Days 30, 60, and 100 (\pm 10 days) after the last dose of study therapy or should coincide with the date of discontinuation (\pm 10 days) if date of discontinuation is greater than 30 days after the last dose of study therapy to monitor for AEs. All participants will be required to complete one (if participant only received BMS-986205) or three Clinical/Safety Follow-Up visits regardless of whether they start a new anti-cancer therapy, except those participants who withdraw consent for study participation.

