8.1.1 Poststudy Treatment Study Follow-up

In this study, safety and tolerability of BMS-986205 administrated as monotherapy and in combination with nivolumab is a key endpoint of the study. Poststudy follow-up is of critical importance and is essential to preserving participant safety and the integrity of the study. Participants who discontinue study treatment must continue to be followed for collection of outcome for at least 100 days after the last dose of study therapy.

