## **6 STUDY PERIODS, TREATMENT REGIMENS AND POPULATIONS FOR ANALYSES**

### **6.1 Study Periods**

- Baseline period:
  - Baseline evaluations or pre-treatment events will be defined as evaluations or events that occur before the date and time of the first dose of study treatment. Evaluations (laboratory tests, pulse oximetry, vital signs) on the same date and time of the first dose of study treatment will be considered as baseline evaluations. Events (AEs) on the same date and time of the first dose of study treatment will not be considered as pre-treatment events.
  - In cases where the time (onset time of event or evaluation time and dosing time) is missing or not collected, the following definitions will apply:
    - ◆ Pre-treatment AEs will be defined as AEs with an onset date prior to but not including the day of the first dose of study treatment;
    - ◆ Baseline evaluations (laboratory tests, pulse oximetry, vital signs) will be defined as evaluations with a date (and time if collected) on or prior to the date of first dose of study treatment.
  - If there are multiple valid observations in the baseline period, then the latest non missing observation will be used as the baseline in the analyses. If multiple observations exist on the latest collection date (and time if collected), the record with the latest data entry date and time will be used. If multiple observations exist on the latest collection date (and time if collected) and data entry date and time, then the first observation is used as baseline, unless otherwise specified.
- For nivolumab Anti-Drug Antibody (ADA), the baseline record of IDO1 inhibitor immunogenicity (IMG) evaluation must be less than the date and time of the first Nivolumab/IDO1 inhibitor dose date and time.
- Post baseline period:
  - On-treatment AEs will be defined as AEs with an onset date and time on or after the date and time of the first dose of study treatment (or with an onset date on or after the day of first dose of study treatment if time is not collected or is missing). For subjects who are off study treatment, AEs will be included if event occurred within a safety window of 100 days after the last dose of study treatment if a participant received BMS-986205 + NIVO (or 30 days after the last dose of study treatment if a participant received only BMS-986205). No “subtracting rule” will be applied when an AE occurs both pre-treatment and post-treatment with the same preferred term and grade.

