## 6.3 Populations for Analyses

- Enrolled subjects Population: All subjects who signed the informed consent form and obtained a subject number.
- Treated subjects Population: All enrolled subjects who received at least one dose of any study treatment.
- Pharmacokinetic Population: All enrolled subjects who received at least one dose of any study treatment and have any available concentration-time data.
- Evaluable Pharmacokinetic Population: A subset of the PK Population, defined as all subjects who have adequate PK profiles or have at least one evaluable PK parameter. All available derived PK parameter values will be included in the PK data set and reported, but only participants with evaluable PK will be included in the summary statistics.
- Immunogenicity Population: All enrolled subjects who received at least one dose of nivolumab and have a baseline and at least one post-treatment immunogenicity measurement.

Unless otherwise specified, the safety analyses will include all treated subjects.

Unless otherwise specified, the efficacy analyses will include all treated subjects.

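### The 100-day death row in SAP 7.6.1 can be incomplete for participants who received only BMS-986205, because the documents disagree on whether they are followed for 30 or 100 days

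*SAP*

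**What the plan says.** **Analysis.** SAP 7.6.1 summarises all deaths with reasons, then "Deaths within 100 days of last dose received, reasons for death", and adds a by-subject listing of deaths for all enrolled subjects. The lead sentence of SAP 7.6 sets the denominator: "Analyses in this section will be tabulated for all treated subjects by phase (monotherapy lead-in, combination) and overall, unless otherwise specified". SAP 6.3 defines treated subjects as "All enrolled subjects who received at least one dose of any study treatment", so a participant who takes BMS-986205 in Cycle 0 and never receives nivolumab is counted. SAP 7.6.1 makes no exception for such participants.

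**Follow-up.** Protocol 5.1 states: "Participants must be followed for at least 100 days after the last dose of study therapy or 30 days if participant only received BMS-986205". It adds: "All participants will be required to complete one (if participant only received BMS-986205) or three Clinical/Safety Follow-Up visits". Table 2-4 footnote a agrees ("or at Day 30 if participant only received BMS-986205"), as do the synopsis and SAP 2.1. Protocol 9.2.1 ends routine SAE collection at 30 days for participants who do not receive combination therapy. Protocol 8.1.1 differs. Its rule for anyone coming off treatment is that they "must continue to be followed for collection of outcome for at least 100 days after the last dose of study therapy", with no exception for lead-in-only participants.

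**Other windows.** For adverse events and laboratory evaluations, SAP 6.1 does distinguish the two groups: 100 days after combination treatment, "or 30 days after the last dose of study treatment if a participant received only BMS-986205".

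Deaths are named among the primary safety endpoints in protocol Table 4-1 and SAP Table 4-1, without a time window.

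**The concern.** The death row counts over a window that, on one reading of the protocol, runs 70 days past the end of required follow-up for part of its denominator. A lead-in-only participant who dies on Day 60 would be in the denominator but need not be in the numerator. The error has one direction: a missed death can only lower the proportion.

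Such participants are foreseen. Protocol 5.1 lists adverse events that bar entry to Cycle 1, and protocol 5.2 replaces anyone who discontinues before or at Cycle 1 Day 1. They therefore add to the treated set and are not displaced from it. At about 12 to 15 treated participants, one death visibly moves a percentage.

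The tables can also disagree without explanation. For a lead-in-only participant, grade 5 adverse events are counted to Day 30 under SAP 6.1, while deaths are counted to Day 100 under SAP 7.6.1.

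**Working it through.** **1. The plan's own safety figure.** SAP 5 gives a 90% probability of seeing at least one event of 18% incidence in 12 subjects: 1 - 0.82^12 = 0.908. This reproduces and is not in dispute. The documents state no death rate and no expected number of lead-in dropouts.

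**2. Windows for a participant who received only BMS-986205.**

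| Item | Source | Days after last dose |
|---|---|---|
| Death row | SAP 7.6.1 | 100 |
| Adverse events, including grade 5 | SAP 6.1 | 30 |
| Required follow-up | Protocol 5.1, Table 2-4 footnote a, SAP 2.1 | 30 |
| SAE collection | Protocol 9.2.1 | 30 |
| Outcome follow-up after discontinuation | Protocol 8.1.1 | at least 100 |

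Under the 30-day rule the gap is 100 - 30 = 70 days, or 70% of the counting window. With the ±10-day visit allowance it is 60 to 80 days.

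**3. What is captured in the gap.** Protocol 9.2.1 says investigators need not actively seek events in former participants. It does require them to report a later SAE, including a death, that they learn of and consider related. Ascertainment after Day 30 is therefore passive, and deaths judged unrelated, such as deaths from progression, are the ones mainly exposed.

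**4. Chance of a death in the gap (assumed survival).** Take S(t) = exp(-Lt), with L = ln 2 / (median in months × 30.4375), using the SAP 8.1 month length. The chance of death on Days 31-100 is S(30) - S(100).

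| Assumed median | S(30) | S(100) | Difference |
|---|---|---|---|
| 4 months | 0.843 | 0.566 | 0.277 |
| 6 months | 0.892 | 0.684 | 0.208 |
| 12 months | 0.945 | 0.827 | 0.118 |

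**5. Effect on the proportion.** Assume 3 lead-in-only participants among 15 treated, and that every Day 31-100 death is missed.
- 4-month median: 3 × 0.277 = 0.83 deaths; 0.83 / 15 = 5.5 percentage points.
- 6-month median: 3 × 0.208 = 0.62 deaths; 0.62 / 15 = about 4.2 points.
- 12-month median: 3 × 0.118 = 0.35 deaths; 0.35 / 15 = about 2.4 points.

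These are upper bounds on the expected shortfall under the assumptions, because some of the deaths would become known. A single missed death would be 1/15 = 6.7 points, but that is the size of one event and not an expected bias.

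**The case against.** The strongest defence is that protocol 8.1.1 already requires 100 days of outcome follow-up for everyone who discontinues. If sites follow it, SAP 7.6.1 matches the data and nothing is lost. The 30 days in protocol 5.1 is also a minimum, and related deaths remain reportable whenever the investigator learns of them. The endpoint itself carries no window: SAP 7.6.1 also tabulates all deaths and lists each one, so every known death is shown. The 100-day row is one descriptive cut in a small study without a hypothesis test.

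All of this stands, and it limits the point. It does not remove it, because 8.1.1 is contradicted by 5.1, Table 2-4 and 9.2.1, and a site that applies the 30-day rule is following the protocol as written. The all-deaths row and the listing show known deaths; they cannot show deaths that nobody was required to find.

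Two further inferences should be resisted.
- A reader might want the split window of SAP 6.1 copied into the death row. That would drop known Day 31-100 deaths of lead-in-only participants from the row and mix 30-day and 100-day risks in one percentage.
- A reader might extend the point to the 100-day windows for concomitant medications (SAP 7.4.3) and immune-mediated adverse events (SAP 7.1.1.3). The planned outputs for these are by-subject listings (SAP 7.4.3 and 7.6.7), which have no denominator, so no change is needed there on this ground.

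**Conclusion.** The inconsistency is real and worth correcting. The 100-day death row can be incomplete for participants who received only BMS-986205, and any error lowers the proportion. This needs three things: at least one lead-in-only participant, a site that applies the 30-day rule, and a Day 31-100 death that goes unrecorded.

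A reader might infer that the primary death count is incomplete, or biased low. The documents do not support that, because under 8.1.1 the count is complete and the primary endpoint is not tied to the 100-day window. Nor do they show that lead-in dropouts are the sickest participants: that is plausible, but the listed bars to Cycle 1 are toxicity criteria, and entry requires ECOG 0-1 and a life expectancy of at least 3 months.

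The expected shortfall is at most about 2.4 to 5.5 percentage points. It rests entirely on assumed medians of 4 to 12 months, constant hazard, 3 lead-in-only participants of 15, and no capture at all after Day 30.

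**What to change.** 1. Reconcile protocol 8.1.1 with protocol 5.1, Table 2-4 and 9.2.1 on how long lead-in-only participants are followed, and carry the result into SAP 2.1.
2. If 30 days stands, restrict the 100-day death row in SAP 7.6.1 to nivolumab-treated participants and give lead-in-only participants a separate 30-day row. Keep every known death, whenever it occurred, in the all-deaths summary and the listing.
3. If 100 days is required for all, keep the row as planned and report beside it how many participants have known vital status at Day 100.

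The cost is protocol and SAP wording and one table change. The third option also needs a vital-status contact at Day 100 for the few lead-in-only participants, which 8.1.1 already implies. The sample size and its stated precision do not change.
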